6.4.1.2. Safety

The safety data will be analyzed based on nominal visits recorded on eCRF. The safety data collected at the unscheduled visits will be included in the data listings only.

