8.2 Lost to Follow-Up

A subject will be considered lost to follow-up if he/she repeatedly fails to return for scheduled visits and is unable to be contacted by the study site.

The following actions must be taken if a subject fails to return to the clinic for a required study visit:

- The site must attempt to contact the subject and reschedule the missed visit as soon as possible and counsel the subject on the importance of maintaining the assigned visit schedule and ascertain whether or not the subject wishes to end/or will continue in the study.

- Before a subject is deemed lost to follow-up, the PI/TI (or designee) must make every effort to regain contact with the subject (where possible, 3 telephone calls and, if necessary, a certified letter to the subject's last known mailing address or local equivalent methods). These contact attempts will be documented in the subject's medical record.
- If the subject continues to be unreachable, he/she will be considered to have withdrawn from the study with a primary reason of lost to follow-up.

9. Study Assessments and Procedures

- The clinical study shall not begin until the required approvals from the appropriate regulatory authorities and IRBs have been obtained.
- An unscheduled visit may occur for safety purposes (eg, evaluation of AEs or ISRs as requested by the subject and/or TI) or photographic reshoots. Applicable procedures will be performed and recorded on the eCRF.
- Throughout the study, to the extent possible, it is recommended that treatment and safety assessments for a particular subject be performed by the same TI, and effectiveness assessments (ACSS, AFLS, and hydration measurements) be performed by the same EI. If it is not possible to use the same evaluator to follow the subject, it is recommended that evaluations overlap (examine the subject together and discuss findings) for at least 1 visit.
- Where possible, subject questionnaires are to be completed prior to other assessments at each follow-up visit, with the FACE-Q questionnaires completed first.
- Safety e-diaries will ensure that subjects complete diaries on a daily basis by locking entry for prior days once they have passed.
- Study procedures and their timing are summarized in the schedule of activities ([Section 2](#)).
- Protocol waivers or exemptions are not allowed.

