9.5.5 Adverse Events of Special Interest

An AESI is defined as any vision-related AE. See [Section 9.5.1](#) for procedures for reporting an AESI.

9.5.6 **Pregnancy**

If a female becomes pregnant during the study, the PI/TI (or designee) will notify the sponsor immediately after the pregnancy is confirmed. The PI/TI shall (1) instruct the subject to notify her physician of the presence of the investigational device and (2) follow the pregnancy to term or termination. Best practices are to be followed in order to ensure the welfare of the subject and the fetus. The Allergan Medical Safety Physician will contact the PI/TI to obtain information about the pregnancy outcome. The subject will continue to be followed, and the pregnancy will be documented as a protocol deviation.

Pregnancy by itself will not be considered an AE or SAE. Hospitalization for a normal delivery or elective abortion of a normal fetus does not constitute an SAE. However, the occurrence of an adverse pregnancy outcome for the mother or child may constitute an AE or SAE, and these are to be reported as described in [Appendix 12.3](#).

9.5.7 **Medical Device Incidents (Including Malfunctions)**

Incidents fulfilling the definition of an AE/ADE/SAE/SADE will follow the processes outlined in [Section 9.5.3](#) and Appendix 12.3.

In order to fulfill regulatory reporting obligations worldwide, the PI is responsible for the detection and documentation of events meeting the definitions of incident, malfunction, or deficiency that occur during the study with such devices.

The definition of a medical device incident and a device deficiency can be found in [Appendix 12.4](#).

9.5.7.1 **Time Period for Detecting Medical Device Incidents**

- Medical device incidents, deficiencies, or malfunctions of the device that result in an incident will be detected, documented, and reported during all periods of the study in which the medical device is used.
- If the PI (or designee) learns of any incident at any time after a subject has been discharged from the study, and such incident is considered reasonably related to a medical device provided for the study, the PI (or designee) will promptly notify the sponsor.
- The method of documenting medical device incidents is provided in Appendix 12.4, and reporting information is provided in [Section 9.5.7.3](#).

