An AE is defined in accordance with ISO 14155 as “any untoward medical occurrence, unintended disease or injury, or untoward clinical signs (including abnormal laboratory findings) in subjects, users, or other persons, whether or not related to the investigational medical device.” This definition includes events related to the investigational medical device or comparator and events related to the procedures involved except for events in users or other persons, which only include events related to investigational medical devices.

Adverse Device Effect

An ADE is defined in accordance with ISO 14155 as “a adverse event related to the use of an investigational medical device.” This definition includes any AEs resulting from insufficient or inadequate instructions for use, deployment, implantation, installation, or operation, or any malfunction of the investigational medical device as well as any event resulting from use error (per ISO 62366) or from intentional misuse of the investigational medical device.

AE of Special Interest

An AESI (serious or non-serious) is one of scientific and medical concern specific to the sponsor’s study device, which warrants ongoing monitoring and rapid communication by the investigator to the sponsor. Such an event might warrant further investigation in order to characterize and understand it.

The following AESI has been identified for the study treatment in this protocol: vision-related AE.

AESIs must be reported to the sponsor within 24 hours of awareness of the event by completing the appropriate eCR and notifying Allergan study management personnel and the Medical Safety Physician by fax or email. Allergan will notify the FDA of a y AESI within 10 days of Allergan’s awareness of the event.

Events Meeting the AE/ADE Definition

- Any abnormal laboratory test results (hematology, clinical chemistry, or urinalysis) or other safety assessments (eg, ECGs, radiological scans, vital signs measurements), including those that worsen from baseline, considered clinically significant in the medical and scientific judgment of the PI (ie, not related to progression of underlying disease)

- Exacerbation of a chronic or intermittent pre-existing condition including either an increase in frequency and/or intensity of the condition
- New condition detected or diagnosed after study treatment administration even though it may have been present before the start of the study

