5.6.3.1. Adverse Events of Special Interest

ISRs recorded in participant ISRs recorded in participant diaries after each treatment (initial, touch-up and repeat) will be summarized for that treatment, respectively. The diary date and time will be compared with the treatment injection ISRs recorded in participant diaries after each treatment (initial, touch-up and repeat) will be summarized for that treatment, respectively. The diary date and time will be compared with the treatment injection ISRs recorded in participant diaries after each treatment (initial, touch-up and repeat) will be summarized for that treatment, respectively. The diary date and time will be compared with the treatment injection Add analysis for adverse events of special interest. The list of adverse events of special interest can be defined in [Section 6](#) or defined in this section if the list is not too lengthy.

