5.6.6. Other Safety Endpoints

Other safety endpoints include the line change on Snellen visual acuity, confrontation visual fields, ocular motility assessments, and the overall converted score of FACE-Q Recovery Early Life Impact questionnaire (see [Section 6.5.5](#) and [Section 6.5.6](#)).

The number of line change based on Snellen visual acuity will be calculated using the formula below and rounded to the nearest integer. Baseline in the below formula is the pre-treatment value on or before the most recent treatment.

$$\text{Line change} = 10 \times [\log_{10} (d_{\text{baseline}}/20) - \log_{10} (d_{\text{follow-up}}/20)]$$

where d_{baseline} = denominator of the Snellen equivalent unit at baseline,

$d_{\text{follow-up}}$ = denominator of the Snellen equivalent unit at follow-up visit

Line change of visual acuity, confrontation visual fields, and ocular motility assessments assessed by the TI (or designee) will be summarized by descriptive statistics. The overall converted score of FACE-Q Recovery Early Life Impact questionnaire calculated based on the conversion table will be summarized by descriptive statistics.

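### Vision measurements from unscheduled visits are left out of the SAP's vision summaries, and no table counts the protocol's only adverse event of special interest

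*SAP*

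**What the plan says.** **AESI definition.** Protocol 9.5.5 states: "An AESI is defined as any vision-related AE". Protocol Appendix 3 names no other: "The following AESI has been identified for the study treatment in this protocol: vision-related AE". The same appendix requires a report to the sponsor within 24 hours and sponsor notification of the FDA within 10 days.

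**Planned AESI analysis.** SAP 5.6.3.1 carries the AESI title but contains broken, repeated diary text, beginning "ISRs recorded in participant ISRs recorded in participant diaries after each treatment (initial, touch-up and repeat) will be summarized for that treatment, respectively", followed by an instruction to the author: "Add analysis for adverse events of special interest. The list of adverse events of special interest can be defined in" Section 6. Section 6 has no such list. Table 5-8 has no AESI row. SAP 5.6.3 does plan an AESI listing.

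**Planned vision analysis.** SAP 5.6.6: "Line change of visual acuity, confrontation visual fields, and ocular motility assessments assessed by the TI (or designee) will be summarized by descriptive statistics". The baseline for line change is the pre-treatment value on or before the most recent treatment. No worst-value summary is planned.

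**Visit rule.** SAP 6.4.1.2 bases safety analyses on nominal eCRF visits and says: "The safety data collected at the unscheduled visits will be included in the data listings only".

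**Unscheduled visits.** Protocol Section 9: "An unscheduled visit may occur for safety purposes (eg, evaluation of AEs or ISRs as requested by the subject and/or TI"), or for repeat photographs. Applicable procedures are performed and recorded on the eCRF.

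**The concern.** Unscheduled visits exist partly so that a participant or the treating investigator can have a possible adverse event looked at. If vision is tested at such a visit, the result is prompted by a symptom and is of direct interest for the one event that the protocol singles out. The SAP keeps that result out of its vision summaries. The effectiveness rule in SAP 6.4.1.1 is different: its analysis windows take scheduled and unscheduled visits alike.

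The section that should give a second view of the same risk, the AESI analysis, was never written. A reader of the tables would have scheduled-visit vision results on one side and eye-related preferred terms spread through the TEAE tables on the other. Nothing would state how many participants had a vision-related AE in each period.

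**Working it through.** No figure in the plan is in dispute, so the check mainly traces cases through the rules.

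**1. Scheduled vision tests.** Table 2-4 (control group, delayed treatment) marks acuity, fields and motility at initial treatment, Day 3, touch-up, Day 3 after touch-up, and Month 1. Its footnote puts the treatment-day tests before injection and about 30 minutes after. Months 2, 4 and 6 are blank. The cells of Table 2-2 (treatment group) are not in the text available here, so this timing is confirmed only for Table 2-4. The rule in SAP 6.4.1.2 covers both groups.

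**2. Which changes reach the SAP 5.6.6 summaries.** The formula is line change = 10 × [log10(d_baseline/20) − log10(d_follow-up/20)], rounded to an integer.

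- *Present at a scheduled test.* It is measured and summarized. The visit rule does no harm.
- *Arises and resolves between scheduled tests.* Take a hypothetical fall from 20/20 to 20/40, measured at an unscheduled visit the day after injection and back to 20/20 by Day 3. The unscheduled value is 10 × [log10(20/20) − log10(40/20)] = 10 × (0 − 0.301) = −3.01, or −3 lines. Day 3 gives 10 × (0 − 0) = 0. The summaries receive the 0, and the −3 is only listed.
- *Arises after Month 1.* Table 2-4 has no later scheduled vision test. Any study measurement would come from an unscheduled visit and would only be listed, whether or not the change resolves.

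**3. The same case through AE reporting.** SAP 5.6.3 defines a TEAE by when it began or worsened relative to treatment (or randomization, for controls), not by visit. TEAEs are tabulated for CP, TP and RP by SOC, PT and severity, and all TEAEs and AESIs are listed. If recorded as an AE, the case should appear in both places. Two gaps remain:

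- SAP 5.6.3 counts a participant once per PT, so PT rows cannot be added to give a number of participants. The SAP also supplies no terms that identify the AESI.
- Read literally, the safety data in SAP 6.4.1.2 could include AEs first reported at an unscheduled visit. The period-based tables suggest that this is not intended, but the SAP does not say so.

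**4. How many events to expect (context only).** Protocol 10.1 states 95% power to detect a treatment-related AE with 2% incidence in 147 treated participants. The chance of at least one event is 1 − 0.98^147 = 0.949, which agrees. The documents give no rate for vision events. Under assumed rates, 1 − (1 − p)^147 gives:

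| Assumed rate p | Chance of at least one event in 147 |
|---|---|
| 0.1% | 13.7% |
| 0.2% | 25.5% |
| 0.5% | 52.1% |
| 1% | 77.2% |

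At the lower of these rates few events, if any, would be expected, so a single omitted measurement could matter to a descriptive vision summary.

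**The case against.** The strongest reply is that nothing is hidden. Vision is tested at fixed times whatever the symptoms, TEAEs are counted by period, AESIs are listed, and each AESI goes to the sponsor and the FDA on a short clock. Nominal-visit tables with unscheduled values in listings are a coherent, disclosed rule. Item 12 of SAP Appendix 2 shows that the sentence on unscheduled visits was added on purpose. The protocol asks only for a descriptive vision summary, and for very few events a case listing may tell more than a table.

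Much of this stands, and it rules out three stronger readings that a reader might infer:

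- *That the visit tables see participants when well and miss them when symptomatic.* They do not. A participant with symptoms at a scheduled test is included, and an early, lasting deficit would be measured at Day 3 and Month 1.
- *That the report would not show the incidence of vision events.* Events recorded as AEs enter the SOC and PT tables with n (%). What is missing is the combined AESI count.
- *That a real case would be tabulated as a zero incidence.* SAP 5.6.6 specifies no threshold category in which such a zero would be printed.

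It is also fair that testing vision at an unscheduled visit is inferred from the reference to applicable procedures, not required. Protocol 9.5 sends vision loss to a retinal specialist, so the worst measurement may not be a study value at all.

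The reply does not reach two points. Listing a symptom-prompted measurement does not put it in a summary, and a listing is not a count. An instruction left in place of the analysis of the only AESI is not a choice of method.

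**Conclusion.** The concern holds in a limited form. The vision summaries in SAP 5.6.6 would omit a change measured only at an unscheduled visit. Under the Table 2-4 schedule, that means a change that arises and resolves between scheduled tests, or one that arises after Month 1. Separately, and whether or not such a visit occurs, no planned table gives a combined count of vision-related AEs.

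The effect on the vision summaries is the number of participants whose change was measured only off schedule, which the documents do not allow anyone to estimate. It is zero if no unscheduled vision tests take place. The conclusion assumes that applicable procedures at an unscheduled visit can include vision tests and that SAP 6.4.1.2 is applied as written. It does not imply that events would be lost to the report. The effectiveness analyses are untouched. This is an inexpensive improvement worth making before the tables are produced.

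**What to change.** 1. **SAP 6.4.1.2.** Keep the nominal-visit tables. State that the nominal-visit rule does not apply to AEs, which count in the TEAE tables whenever they are reported.
2. **SAP 5.6.6.** Add, for each treatment (initial, touch-up, repeat), a worst post-treatment vision summary that uses scheduled and unscheduled assessments and the baseline already defined there. Give n (%) by line-change category, and n (%) with any new visual-field or motility abnormality. Fix the categories in advance; line change is already rounded to whole lines.
3. **SAP 5.6.3.1.** Delete the stray text and the instruction. Insert the definition from protocol 9.5.5, say how qualifying events are identified, and give n (%) for CP, TP and RP in the populations that SAP 5.6.3 already uses.
4. **Table 5-8.** Add the AESI row.

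The cost is SAP wording, one table row and a few small tables from data that the eCRF records where the tests are done. The downside is that a worst value picks up measurement noise, more so for participants who are tested more often. The new summary should therefore stand beside the nominal-visit tables, not replace them.

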6.4.2. Missing Date Imputation

Missing date will be imputed for TEAEs and medications. The missing AE dates will be imputed with year, month, and day values based on the corresponding scenarios in [Table 6-5](#) and algorithms described in [Sections 6.4.2.1](#) and [6.4.2.2](#). If the AE stop date is complete and the imputed AE start date is after the stop date, the AE start date will be re-imputed using the stop date. If the imputed AE stop date is before the start date (imputed or non-imputed start date), the start date will be the imputed stop date.

The missing medication start and stop dates will be imputed based on the algorithms described in [Sections 6.4.2.3](#) and [6.4.2.4](#). When the medication start date and stop date are both incomplete for a participant, the start date will be imputed first. If the medication stop date is complete and the imputed start date is after the stop date, the start date will be imputed using the stop date. If the imputed medication stop date is before the start date (imputed or non-imputed start date), the start date will be the imputed stop date.

Table 6-5 **Imputation Scenarios**

Scenario	Complete			Imputable
	Year	Month	Day	
1	Yes	Yes	Yes	N/A
2	Yes	Yes	—	Yes
3	Yes	—	Yes	No ^a
4	Yes	—	—	Yes
5	—	Yes	Yes	No ^a
6	—	Yes	—	No ^a
7	—	—	Yes	No ^a
8	—	—	—	Yes

^a Not allowed per database design.

6.4.2.1. Missing/Incomplete AE Start Date

For scenario 2 from Table 6-5 (if day is missing but month and year are available), then the imputed day will be the first day of the month or the date of first study treatment (which will be the date of randomization for control group) if they have the same month and year, whichever is later (because TEAE onset is not expected prior to administration of study treatment).

For scenario 4 (if day and month are missing but year is available), then the imputed day and month will be 01 Jan or the date of first study treatment (or date of randomization for control group) if they have the same year.

For scenario 8 (if day, month and year are all missing), impute start date as the latter of randomization date or first study treatment date.

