5.1. General Considerations

- The primary analysis will be performed after the database is locked and randomization schedule is released.
- To account for different timing of VOLITE treatment and comparable time frame of data collection to enhance interpretability of effectiveness and safety analyses, the statistical analyses will be performed by the study periods defined below in [Table 5-1](#). For participants randomized to the treatment group, the Treated Period (TP) is the Control Period (CP) plus the Follow-up Period; for participants randomized to the control group, the TP is the Follow-up Period composed of the delayed treatment period plus the delayed treatment follow-up period ([Figure 1-1](#)). Follow-up Period starts on the end date of CP + 1 and ends on the same day as TP.

Table 5-1 Definition of the Control, Treatment, and Repeat Treatment Periods by Randomization Group

Randomization Group	Period	Treatment Group Label	Start Date	End Date
Treatment	Control Period (CP)	VOLITE	Initial treatment date	
The end date is the date of the Month 1 assessment:
 
 • If multiple assessments fall into Month 1 window, the date of the assessment included in the Month 1 analysis will be used as end date. • For participants who exit before Month 1, the end date is study exit date. • For participants with a missing assessment at Month 1, the end date is the target day for Month 1.
	Treated Period (TP)	VOLITE	Initial treatment date	Date of repeat treatment or the study exit date, whichever is earlier
	Repeat Treatment Period (RP)	VOLITE	Repeat treatment date	Study exit date
Control	CP	Control	Randomization date	
For participants who do not receive optional treatment:
 
 • If multiple assessments fall into Month 1 window, the date of the assessment included in the Month 1 analysis will be used as end date. • For participants who exit before Month 1, the end date is study exit date. • For participants with missing assessment at Month 1, the target day for Month 1 (Day 31) will be the end date. 
For participants who receive optional treatment: the end date is the date of optional treatment.

	TP	VOLITE Post-Control	Optional treatment date	Study exit date

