5.6.3. Adverse Events

An AE will be considered a treatment emergent adverse event (TEAE) if the AE began or worsened (increased in severity or became serious) after first administration of VOLITE for the treatment group and after the date of randomization for the control group. A TESAE is defined as an SAE that is also a TEAE. Overall summary will be provided on a per-participant level for TEAEs, treatment-related TEAEs, TESAEs, deaths, and TEAEs leading to study intervention discontinuation.

If more than one event is coded to the same PT for the same participant, the participant will be counted only once for that PT using the greatest severity for the summarizations by severity and most related occurrence for the summarizations by relationship to study intervention. If the severity of a TEAE is missing, the maximum severity will be assigned to the event for the summarization by severity. The value will be displayed as missing in the data listing. If the relationship to the study intervention is missing for a TEAE, the event will be considered related to the study intervention for the summarization. The value will be displayed as missing in the data listing.

TEAEs will be summarized by treatment group for CP using the Safety population. TEAEs will also be summarized for TP and RP using the VT and VRT populations, respectively.

The number and percentage of participants with TEAEs and the events in the following AE categories will be summarized for the above populations as described in [Table 5-8](#). For participants who received repeat treatment, their AEs reported during the first month in the initial treatment period will be summarized and presented in parallel with AEs reported during the repeat treatment period.

JUVÉDERM VOLITE™ XC

Summary tables will be provided for participants with TESAEs and participants with TEAEs leading to discontinuation if these occurred in 5 or more participants. Listings of all TEAEs, AESIs, TESAEs, TEAEs leading to discontinuation, and death will be presented.

Table 5-8 **TEAE Summaries**

Endpoint	Description	Timing	Methodology

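### Partial AE start dates for crossed-over controls are anchored on randomization, so some events after the optional VOLITE injection would fall in the untreated Control period

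*SAP*

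**What the plan says.** SAP 6.4.2.1 imputes an incomplete AE start date according to what is missing.

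- Day missing (scenario 2): the later of the first of the month and the "date of first study treatment (which will be the date of randomization for control group) if they have the same month and year". The reason given is "because TEAE onset is not expected prior to administration of study treatment".
- Day and month missing (scenario 4): "01 Jan or the date of first study treatment (or date of randomization for control group) if they have the same year".
- Whole date missing (scenario 8): "impute start date as the latter of randomization date or first study treatment date".

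The analysis periods are set in SAP 5.1. For a control who crosses over, Table 5-1 closes the Control Period (CP) at the injection: "For participants who receive optional treatment: the end date is the date of optional treatment". The Treated Period (TP), labelled VOLITE Post-Control, opens on that same date. The accompanying text says that "for participants randomized to the control group, the TP is the Follow-up Period composed of the delayed treatment period" and its follow-up.

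SAP 5.6.3 counts an AE as treatment-emergent if it began or worsened "after first administration of VOLITE for the treatment group and after the date of randomization for the control group". It then says: "TEAEs will be summarized by treatment group for CP using the Safety population". The TP and repeat-period (RP) tables use the VT and VRT populations.

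**The concern.** The rule is meant to stop an undated AE from being placed before treatment. It does this for the treatment group, where randomization and first injection fall on the same day (Protocol Table 2-2, footnote e). For the control group the anchor is a date on which nothing is injected. The optional injection is offered only after a month without treatment (Protocol Table 2-4, footnote a), so it normally falls in a later calendar month. The anchor then has no effect, and the date defaults to the 1st, before the injection.

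At stake is where such an event is tabulated. An AE that followed a VOLITE injection could leave the VOLITE Post-Control column and appear in the untreated Control column, which is the comparator in the only randomized safety comparison. Time to onset of treatment-related TEAEs (SAP Table 5-8) would also be wrong for that event. SAP 5.6.3 treats missing severity and missing relatedness conservatively. This date rule errs the other way.

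**Working it through.** The plan gives no figure to reproduce. The check applies the rules as written.

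**Inputs**
- Imputation rules: SAP 6.4.2.1. Period boundaries: SAP Table 5-1.
- Randomization to optional injection: 28 to 44 days, from the visit windows in Protocol Tables 2-3 and 2-4 (30 − 2 = 28; 30 + 7 + 7 = 44).
- Controls expected to be treated: 28 (SAP 3).
- Assumed, not in the documents: onset spread evenly over a stated number of days from injection, with injections spread evenly over the calendar.

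**1. Example.** A control is randomized on 20 March and injected on 22 April.
- AE recorded as April: the month differs from randomization, so onset is 1 April, 21 days before injection, in CP.
- Same record for a treatment-group participant injected on 22 April: onset is 22 April.
- AE recorded by year only, in that year: onset is 20 March, in CP.
- AE recorded as May: onset is 1 May, correctly in TP.

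**2. Which dates move.** In scenario 2, only onsets in the calendar month of the injection move, and not if the injection was on the 1st. In scenario 4, the dates that move are those in the injection year, unless the injection was on 1 January. They are set to randomization if it is in that year, otherwise to 1 January.

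**3. Share of post-injection AEs misplaced.** Let m be the mean number of days from injection to onset.
- Scenario 2, onsets within 30 days: about 1 − (m + 1)/30.4. For 7, 14 and 30 days, m = 3, 6.5 and 14.5, giving 87%, 75% and 49%.
- Scenario 2, onsets over 211 days (about 7 months): on average 14.7 of those days lie in the injection month, excluding injections on the 1st. 14.7/211 = 7%.
- Scenario 4: about 1 − (m + 1)/365, giving 99%, 98%, 96% and, with m = 105, 71%.

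Counting every randomization day in a year, with gaps of 28, 30, 37 and 44 days, gives the same percentages.

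**4. Number of events.** Assume 1 to 3 post-injection AEs per crossover and 2% to 5% with partial dates.
- Partial dates: 28 × 1 × 0.02 = 0.56 to 28 × 3 × 0.05 = 4.2.
- If all lack only the day: 0.56 × 0.07 = 0.04 to 4.2 × 0.87 = 3.7 events moved.
- If all are year-only: 0.56 × 0.71 = 0.4 to 4.2 × 0.99 = 4.2 events moved.

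One participant moved changes an incidence by at most 1/28 = 3.6 percentage points in VOLITE Post-Control and 1/70 = 1.4 in Control (70 = 210/3).

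**5. Existing check.** The stop-date rules in SAP 6.4.2 only pull a start date earlier. They cannot move one forward to the injection.

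**6. Anchoring on the optional injection instead.** Misplacement of true post-injection AEs falls to 0% in scenarios 2 and 4. In return, before any stop-date check, true pre-injection AEs with partial dates move into TP: 49% (gap 30 days) or 40% (gap 37 days) in scenario 2, and 96% or 95% in scenario 4.

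**The case against.** The strongest reply has four parts.

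- **Period assignment is inferred.** The SAP never says outright that imputed onset decides CP or TP, and SAP 6.4.1.2 analyses safety data by nominal visit. The first half stands, and the conclusion is conditional on it. The nominal-visit rule is an unlikely alternative: it suits visit-based measures such as the vision tests, while AEs are monitored continuously, and imputing AE dates would serve little purpose if the dates were not used.
- **Few events are exposed.** AEs are asked about at every post-baseline visit (Protocol 9.5), including Day 3 and Day 30 after injection. Injection site responses are recorded in a daily e-diary and matched to the injection by date and time (SAP 5.6.4), so those summaries do not depend on this rule. This stands, and limits the size.
- **The harm is limited and visible.** The AE summaries are descriptive, with no between-group test. All TEAEs are listed, and a device-related event under Control would look odd. This stands as mitigation, but the tables would still be wrong.
- **Any fixed anchor misplaces something.** This is true, as step 6 of the working shows. The choice is between two imperfect conventions, and for a safety table the conservative one is easier to defend.

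A reader might infer that every partially dated AE after the optional injection ends up in Control. The documents do not support that. With the month known, only injection-month onsets move, and scenario 8 can be read as already giving the optional injection date. A reader might also extend the fault to repeat treatment. There an event would shift between TP and RP, both on VOLITE, and add nothing to Control.

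**Conclusion.** The point holds in limited form. SAP 6.4.2.1 makes no exception for controls who receive optional VOLITE, and in scenarios 2 and 4 it can place their post-injection AEs before the injection, against its own stated reason. If imputed onset assigns the period, those events move from VOLITE Post-Control to untreated Control, in the direction that favours the device.

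The size is probably very small: about 28 participants, and roughly 0 to 4 events under the assumed AE counts and partial-date rates. The documents give neither of those inputs, so they do not support inferring a material distortion of the safety profile. The effectiveness analyses are not affected. Scenario 8 should be reconciled, because its first study treatment date may mean the optional injection, while scenario 2 equates that term with randomization for controls. This is a correction worth making before the tables are run, not a threat to the trial's conclusions.

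**What to change.** In SAP 6.4.2.1, add a rule for control participants who received optional VOLITE:

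- If the partial date shares the month and year (scenario 2) or the year (scenario 4) of the optional injection, and no known stop date precedes that injection, impute the optional injection date. Label this a conservative safety convention. If the eCRF collects a before/after-injection indicator, use that instead.
- State that an onset imputed to the injection date counts in TP, because Table 5-1 ends CP and starts TP on the same date.
- State that in scenario 8 the first study treatment date means the optional injection for these participants.
- State explicitly that imputed onset assigns AEs to CP, TP and RP.

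Leave the handling of repeat treatment unchanged. Anchoring there on the repeat injection would move year-only AEs of the treatment group out of CP and TP into RP, and so remove them from the VOLITE column of the randomized comparison.

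The cost is a few lines of SAP text and code. Some true pre-injection AEs will be counted under VOLITE, so its AE rate may look slightly less favourable. The stop-date condition reduces this but does not remove it.
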